## 1. PROTOCOL SYNOPSIS

Protocol title	Evaluation of novel molecular assays for the detection of influenza virus
Hypothesis	Our novel molecular assays for the detection of influenza A virus will be non-inferior to current molecular assays published by the World Health Organization and the US Centers for Disease Control and Prevention
Primary objective	To evaluate the sensitivity and specificity of different molecular assays
Clinical specimens	Nasopharyngeal and saliva specimens previously tested for influenza A virus
Study design	We will randomly retrieve archived nasopharyngeal and saliva specimens that were previously tested for influenza A virus using commercially available assays in our laboratory, tested for influenza A virus at the Public Health Laboratory Service Branch in Hong Kong. These specimens will be tested for influenza A virus by 4 different RT-PCR assays as listed below: 

1. Our new RT-PCR assay targeting PB2 gene

2. Our new RT-PCR assay targeting NS gene

3. M gene RT-PCR published by the World Health Organization

4. M gene RT-PCR published by the US CDC.

Primary outcome	Results of different RT-PCR assays
Secondary outcome	Cycle threshold (Ct) value of different RT-PCR assays
Data analysis	Sensitivity, specificity, positive predictive value and negative predictive value will be determined

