## 2. BACKGROUND

Seasonal influenza virus causes an estimated 0.3-0.6 million deaths per year. Avian influenza virus H5N1, H7N9 and H5N6 has fatality rate of over 30% [1-3]. Swine influenza viruses from pigs have also infected humans [4].

Molecular assays are now used routinely in the detection of influenza viruses. The M gene is often used as the target for all influenza A viruses because the nucleotide sequence of this gene is relatively conserved among all the influenza A viruses. The World Health Organization and the US Centers for Disease Control and Prevention (CDC) have published protocols for molecular detection of influenza A virus M gene [5, 6].

However, recent studies have shown that mutations in the M gene have led to a reduced sensitivity of RT-PCR assay targeting this gene [7, 8]. Therefore, it is important to use

alternative conserved genes as the target of RT-PCR. In this study, our aim is to evaluate two new RT-PCR assays that are based on PB2 and NS gene segment.

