### **3. STUDY OBJECTIVES**

1. To evaluate the sensitivity and specificity of different molecular assays

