### **4. STUDY DESIGN**

#### **4.1. Overall study design**

We will randomly retrieve archived nasopharyngeal and saliva specimens that were previously tested for influenza A virus using commercially available assays in our laboratory, tested for influenza A virus at the Public Health Laboratory Service Branch in Hong Kong. These specimens will be tested for influenza A virus by 4 different RT-PCR assays as listed below:

1. Our new RT-PCR assay targeting PB2 gene
2. Our new RT-PCR assay targeting NS gene
3. M gene RT-PCR published by the World Health Organization
4. M gene RT-PCR published by the US CDC.

Sensitivity and specificity will be determined as we described previously [9].

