#### **4.2. Outcome measurements**

##### ***4.2.1. Primary outcome measure***

1. Results of different RT-PCR assays

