## 7. STATISTICAL METHODS

### **7.1 Sample size**

We will perform all 4 RT-PCR assays on a total of 320 specimens, including

- 80 nasopharyngeal specimens which tested positive for influenza A by commercially-available molecular assays or by testing performed at the Public Health Laboratory Services Branch in Hong Kong
- 80 nasopharyngeal specimens which tested negative for influenza A by commercially-available molecular assays or by testing performed at the Public Health Laboratory Services Branch in Hong Kong

- 80 saliva specimens which tested positive for influenza A by commercially-available molecular assays
- 80 saliva specimens which tested negative for influenza A by commercially-available molecular assays

The sample size is based on feasibility of the study

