## **7.2 Analysis of the study**

Sensitivity, specificity, positive predictive value and negative predictive value will be calculated for

1. All specimens
2. Nasopharyngeal specimens only
3. Saliva specimens only

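### The protocol's only hypothesis is non-inferiority, but it gives no margin, no measure for the claim and no between-assay comparison, so the stated analysis cannot decide it

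*Protocol*

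**What the plan says.** - **Hypothesis (Protocol, section 1, Hypothesis row).** "Our novel molecular assays for the detection of influenza A virus will be non-inferior to current molecular assays published by the World Health Organization". A US CDC assay is named as the second comparator. This is the only hypothesis, and non-inferiority is not mentioned again.
- **Objective (section 3).** "To evaluate the sensitivity and specificity of different molecular assays".
- **Primary outcome (section 4.2.1).** "Results of different RT-PCR assays".
- **Analysis (section 1, Data analysis row).** "Sensitivity, specificity, positive predictive value and negative predictive value will be determined". Section 7.2 repeats this for all specimens, nasopharyngeal specimens only and saliva specimens only.
- **Method (section 4.1).** "Sensitivity and specificity will be determined as we described previously", with a reference to an earlier study that is not at hand. The sentence mentions neither a margin nor a comparison.
- **Sample size (section 7.1).** "We will perform all 4 RT-PCR assays on a total of 320 specimens": four groups of 80, by specimen type and earlier result, on grounds of feasibility.

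**The concern.** A non-inferiority hypothesis is defined by a measure, a comparator and a margin. The protocol names the comparators and omits the other two. It also leaves open whether each new assay (PB2, NS) must be non-inferior to both M-gene assays or to one of them.

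The objective, primary outcome and analysis are all descriptive and treat each assay separately. The hypothesis and the analysis therefore do not match within the same document. Separate accuracy figures cannot settle the question even once a margin is supplied, because the precision of a paired difference depends on how often the two assays disagree on the same specimen.

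What is at stake is whether the conclusion can be trusted. The data for a paired comparison will exist, but a margin picked once the results are known can be fitted to them, and later analysis cannot restore pre-specification.

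**Working it through.** **1. The plan's own figure.** 4 × 80 = 320, as stated in section 7.1. By earlier result this is 80 + 80 = 160 positive and 80 + 80 = 160 negative specimens. No alpha, power, margin or expected rate is given, so 320 cannot be linked to the hypothesis. The feasibility basis is not counted as a separate error.

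**2. What a decision needs and what the protocol gives.**

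| Element | In the protocol |
|---|---|
| Comparators | Named (WHO and US CDC M-gene assays) |
| Must both be met? | Not stated |
| Measure for the claim | Sensitivity and specificity are the objective; neither is tied to the hypothesis |
| Margin | Not stated |
| New-versus-published contrast | None |
| Decision rule | None |

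**3. How far the verdict depends on the margin.** Assumed: margins of 3, 5 and 10 points and a two-sided Tango 95% interval for paired proportions. Nothing is assumed about true accuracy. Let n = 160, b = gains (new assay positive, M-gene assay negative) and c = losses (the reverse).

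With b = 0 and few losses, the Tango lower limit equals minus the upper Wilson limit for c/n:

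lower limit = −[c + z²/2 + z·√(c(n − c)/n + z²/4)] / (n + z²), with z = 1.96.

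For c = 3: −[3 + 1.921 + 1.96·√(2.944 + 0.960)] / 163.84 = −8.79/163.84 = −5.37 points.

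| Losses (no gains) | Observed difference, points | Tango lower 95% limit, points |
|---|---|---|
| 0 | 0 | −2.34 |
| 1 | −0.6 | −3.45 |
| 2 | −1.25 | −4.44 |
| 3 | −1.9 | −5.37 |
| 8 | −5.0 | −9.56 |
| 9 | −5.6 | −10.34 |

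The largest number of losses that passes is 0 at 3 points, 2 at 5 points and 8 at 10 points. So 3 to 8 losses (3/160 = 1.9% to 8/160 = 5.0%) fail at 5 points and pass at 10.

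**4. Why separate sensitivities are not enough.** Take a net deficit of 3 in 160 (−1.9 points), reached through different discordant counts. The Wald limit is [(b − c) − 1.96·√((b + c) − (b − c)²/n)] / n.

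| Gains/losses | Wald lower limit, points | Tango lower limit, points |
|---|---|---|
| 0/3 | −4.0 | −5.4 |
| 2/5 | −5.1 | −6.0 |
| 5/8 | −6.3 | −6.9 |

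The three cases can share the same two sensitivities, yet the limits differ. At 5 points the 0/3 case passes by Wald and fails by Tango, so the interval method also needs fixing beforehand.

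**5. Power under assumptions not in the protocol.** One-sided 2.5%, Tango score test, n = 160, one comparison at a time, exact enumeration of gains and losses.

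| True state, margin | Discordance 2% | 5% | 10% |
|---|---|---|---|
| Equal assays, 5 points | 91% | 69% | 45% |
| Equal assays, 10 points | 100% | 99.7% | 96% |
| New assay 2 points better, 5 points | 100% | 95.5% | 75% |

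The last row uses gains/losses of 2/0%, 3.5/1.5% and 6/4%. It reflects the Background's premise that "recent studies have shown that mutations in the M gene have led to a reduced sensitivity of RT-PCR assay targeting this gene"; the 2 points are an assumption.

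**The case against.** - **The detail may sit in a statistical analysis plan that is not shown.** This stands for the interval method, which can be left there. It does not stand for the margin and the measure, because they define the hypothesis that the protocol itself states. Nor is the protocol silent on analysis: sections 1 and 7.2 set one out, and it is descriptive.
- **The method is taken from a cited study.** That source cannot be checked here. The sentence in section 4.1 covers only how sensitivity and specificity are determined.
- **The measures are evident, since the objective names sensitivity and specificity.** They are the natural candidates. Whether one or both must be met, and against one comparator or both, stays open.
- **The study is really descriptive, and non-inferiority appears only once.** If so, the hypothesis is wrongly worded and must change. This supports the second remedy and does not remove the mismatch.
- **The evidence is not lost, because any reader could apply a margin to reported paired tables.** True if those tables are reported, but the protocol does not plan them. The pre-specified status of the claim would still be lost.
- **The illustrations rest on assumptions.** This stands. By Wald limits with no gains, up to 4 losses pass at 5 points and up to 9 at 10 points, so the range whose verdict changes is 5 to 9 losses instead of 3 to 8. Either way the verdict turns on an unstated margin. The power figures do not show that 320 specimens are too few. The calculations use the pooled 160; the analyses by specimen type would have 80 each.

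**Conclusion.** The concern holds. The trial's only hypothesis cannot be decided by the analysis the protocol states, because the margin, the measure and the between-assay contrast are all absent. This follows from the text alone and needs no assumption.

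The size of the effect is conditional. With 160 specimens, no gains and a Tango 95% interval, the verdict for 3 to 8 losses reverses between margins of 5 and 10 points. Power for truly equal assays runs from 45% to 91% at 5 points and from 96% to 100% at 10 points, for assumed discordance of 10% down to 2%. This must be settled before testing: it concerns the sole hypothesis, and a margin set after the results are known has no pre-specified standing.

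**What to change.** Choose one of two routes before the specimens are tested.

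**(a) Keep the non-inferiority claim.** State the margin, the measure or measures it applies to, and whether both M-gene comparators must be met. Add to section 7.2 the paired difference (new minus M-gene assay) in sensitivity on the 160 specimens that earlier tested positive, and in specificity on the 160 that earlier tested negative, each with a 95% confidence interval for paired proportions by a named method. Declare non-inferiority only if the lower limit lies above minus the margin. State the power that the fixed specimen numbers give.

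**(b) Drop the claim.** Restate the hypothesis row as an aim to estimate paired differences between assays with 95% confidence intervals, and draw no non-inferiority conclusion.

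The cost is protocol wording and a short extra analysis of data that will be produced anyway, with no more specimens. Route (a) may mean stating low power openly; route (b) gives a weaker claim.

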## 2. BACKGROUND

Seasonal influenza virus causes an estimated 0.3-0.6 million deaths per year. Avian influenza virus H5N1, H7N9 and H5N6 has fatality rate of over 30% [1-3]. Swine influenza viruses from pigs have also infected humans [4].

Molecular assays are now used routinely in the detection of influenza viruses. The M gene is often used as the target for all influenza A viruses because the nucleotide sequence of this gene is relatively conserved among all the influenza A viruses. The World Health Organization and the US Centers for Disease Control and Prevention (CDC) have published protocols for molecular detection of influenza A virus M gene [5, 6].

However, recent studies have shown that mutations in the M gene have led to a reduced sensitivity of RT-PCR assay targeting this gene [7, 8]. Therefore, it is important to use

alternative conserved genes as the target of RT-PCR. In this study, our aim is to evaluate two new RT-PCR assays that are based on PB2 and NS gene segment.

### **3. STUDY OBJECTIVES**

1. To evaluate the sensitivity and specificity of different molecular assays

### **4. STUDY DESIGN**

#### **4.1. Overall study design**

We will randomly retrieve archived nasopharyngeal and saliva specimens that were previously tested for influenza A virus using commercially available assays in our laboratory, tested for influenza A virus at the Public Health Laboratory Service Branch in Hong Kong. These specimens will be tested for influenza A virus by 4 different RT-PCR assays as listed below:

1. Our new RT-PCR assay targeting PB2 gene
2. Our new RT-PCR assay targeting NS gene
3. M gene RT-PCR published by the World Health Organization
4. M gene RT-PCR published by the US CDC.

Sensitivity and specificity will be determined as we described previously [9].

#### **4.2. Outcome measurements**

##### ***4.2.1. Primary outcome measure***

1. Results of different RT-PCR assays

##### ***4.2.2 Secondary outcome measure:***

1. Cycle threshold (Ct) value of different RT-PCR assays

#### **4.3. Confidentiality of data**

The specimens will be tested in an anonymous manner.

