## 6. STUDY PROCEDURES

### **6.1 Nucleic acid extraction and real-time reverse transcription-polymerase chain reaction (RT-PCR) for influenza A virus**

Saliva and nasopharyngeal specimens will be subjected to total nucleic acid (TNA) extraction by NucliSENS easyMAG (BioMerieux, Boxtel, Netherlands) as we described previously [10]. Briefly, 250 µL of each specimen will be mixed with lysing buffer. After extraction, the nucleic acids will be recovered using 55 µL of elution buffer.

Monoplex real-time RT-PCR assays for influenza A virus will be performed using QuantiNova Probe RT-PCR Kit (QIAGEN, Hilden, Germany). The reagent mixture (20 µL) will contain 1x QuantiNova Probe RT-PCR Master Mix, 1x QN Probe RT-Mix, 0.8 µM of each forward and reverse primer, 0.2 µM of probe and 5 µL of TNA as the template. The thermal cycling conditions will be 10 min at 45 °C for reverse transcription, 5 min at 95 °C for PCR initial activation, and 50 cycles of 5 s at 95 °C and 30 s at 55 °C. All reactions will be performed using the LightCycler 480 Real-Time PCR System (Roche, Basel, Switzerland). The primers and probes for the M gene RT-PCR have been published by the WHO and the US CDC [5, 6].

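### Does anonymous testing leave the assay readers unmasked to the earlier influenza A result?

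*Protocol*

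**What the plan says.** The protocol's Section 7.1 plans as follows: "We will perform all 4 RT-PCR assays on a total of 320 specimens, including" four groups set by specimen type and earlier result. For nasopharyngeal specimens these are "80 nasopharyngeal specimens which tested positive for influenza A by commercially-available molecular assays or by testing performed at the Public Health Laboratory Services Branch" and "80 nasopharyngeal specimens which tested negative for influenza A by commercially-available molecular assays or by testing performed at the Public Health Laboratory Services Branch". For saliva they are "80 saliva specimens which tested positive for influenza A by commercially-available molecular assays" and "80 saliva specimens which tested negative for influenza A by commercially-available molecular assays". Section 4.1 describes the archive as specimens "previously tested for influenza A virus using commercially available assays in our laboratory", and also names the public health laboratory. Retrieval from the archive is random.

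On handling, Section 4.3 (Confidentiality of data) has one sentence: "The specimens will be tested in an anonymous manner". Section 6.1 describes extraction and a real-time instrument run of "50 cycles of 5 s at 95 °C and 30 s at 55 °C", and gives no rule for calling a reaction positive. The assay result is the primary outcome (4.2.1) and the Ct value is secondary (4.2.2). The synopsis states a hypothesis of non-inferiority of the two new assays to the two published M gene assays.

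**The concern.** Whoever assembles the four groups must know the earlier result of all 320 specimens. Some of those results probably came from the study laboratory itself. Random retrieval decides which specimens are taken, not who knows their status. Anonymity removes the patient's identity, but an unnamed tube can still sit in a rack of known positives, and anonymity does not hide one assay's result from the person reading the next.

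Two of the four assays are the investigators' own, and 50 cycles leave room for late or weak curves. If these were called with status known, sensitivity and specificity could both be flattered. If this happened more for the new assays than for the comparators, the non-inferiority comparison would shift as well. Masking is laboratory conduct, so an analysis plan written later could not restore it.

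**Working it through.** **Counts (Section 7.1).** Positives: 80 + 80 = 160. Negatives: 80 + 80 = 160. Total: 4 x 80 = 320, as the protocol states.

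**Value of one changed call.**
- Within one specimen type and status: 1/80 = 1.25 points.
- Pooled over both types: 1/160 = 0.625 points.

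**Gain from reading with status known, for one assay.** The protocol does not say how many late curves to expect. Assume m in each status group of 160. Let a and b be sensitivity and specificity when every late curve is called negative. Suppose a cut-off fixed in advance calls k of the m late curves positive among the positives, and j of the m among the negatives.
- Fixed cut-off: sensitivity + specificity = (a + k/160) + (b - j/160) = a + b + (k - j)/160.
- Status known, with every late curve called to agree with the earlier result: (a + m/160) + b = a + b + m/160.
- Gain: (m - k + j)/160.

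| Case | Gain | m = 1 | m = 4 |
|---|---|---|---|
| Cut-off separates the groups (k = m, j = 0) | 0 | 0 points | 0 points |
| Late curves treated alike (k = j) | m/160 | 0.625 points | 2.5 points |
| Cut-off exactly wrong (k = 0, j = m) | 2m/160 | 1.25 points | 5.0 points |

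The gain therefore has no fixed size. It depends on m, k and j, none of which the protocol gives, and its lower end is zero.

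**Effect on the comparison of assays.** All four assays are run on the same specimens. If knowledge of status changes d1 calls for a new assay and d2 for a comparator among the 160 positives, the difference in sensitivity moves by (d1 - d2)/160. With d1 = d2 it does not move. Only unequal steering biases the comparison, and nothing in the protocol indicates how unequal it might be.

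**What must hold for harm, against the text.**
1. *Readers know the status.* Section 4.3 speaks of how specimens are tested, not only of how data are stored. A tester with an unidentified tube cannot look up its earlier result by patient. A laboratory that holds records is not the same as an operator who knows a given tube's status. The protocol shows neither that readers are masked nor that they are not.
2. *Calls are open to judgement.* Section 6.1 gives no positivity rule, but Section 4.1 refers to a published method for determining sensitivity and specificity. Laboratory procedures commonly hold such rules too. The real-time readout comes largely from the instrument.
3. *Steering differs between assays.* The text does not bear on this.

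All three are needed for a biased comparison, and the first two for a biased estimate for one assay. The protocol establishes none of them.

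**The case for a change.** The best case for acting is that the single handling sentence addresses identity, that no section mentions masking, coding or test order, and that the investigators have an interest in two of the assays. Securing masking would be cheap: study codes, mixed plates and withheld results for the 320 x 4 = 1,280 reactions already planned. Recording Ct values lets cut-offs be rechecked later, but does not undo an unmasked first call or a selective decision to repeat a test.

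Much of this stands. The protocol does not spell out masking, an analysis plan would not normally supply it, and explicit wording would be good reporting. But the case shows silence, not a wrong instruction. It has to allow that anonymous testing may already mean coded testing and that a positivity rule may exist elsewhere. The point that the laboratory's own records cover the 160 saliva specimens (160/320 = 50%) adds little: Section 5.1 does not say where the commercial assay was run, and what matters is what the reader knows, not what the laboratory holds.

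**Conclusion.** No change to the plan is needed. Following the protocol as written, with specimens tested anonymously and read on a real-time instrument, is not shown to give a wrong result. What is missing is a detail that a diagnostic laboratory would normally settle by coding and mixing specimens and applying its standing rule for a positive. A sentence saying so would do no harm, but the validity of the design does not turn on it.

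The unit of risk is 1.25 points per changed call within a specimen type, or 0.625 points pooled. Assuming 1 to 4 late curves per status group, the pooled gain in sensitivity plus specificity lies between 0 and 2m/160, that is, at most 1.25 points for m = 1 and 5.0 points for m = 4. That upper end needs a cut-off that misplaces every late curve. These figures rest on an assumed m and on readers who know the status, which the protocol does not show. The conclusion would change if anonymous testing meant only that patient names were removed while the positive or negative group stayed visible to the reader, and no positivity rule had been fixed beforehand.

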#### **4.4. Archive of data**

The investigator will retain all study documentation pertaining to the conduct of the study at the study site for a period of at least 5 years.

#### **4.5. Ethical endorsement**

The use of archived clinical specimen for microbiological testing has been approved by the Institutional Review Board (IRB) of the University of Hong Kong and Hospital Authority.

